6.4 Efficacy and Safety Variables

6.4.1 Efficacy Variables

6.4.1.1 Primary Efficacy Endpoints

Two primary endpoints will be tested in the following order using hierarchical fixed sequence testing:

1. Change from baseline (CFB) in tCFS (NEI scale) at Day 57
2. CFB of Dryness Score (VAS Severity of Dryness) at Day 57

6.4.1.2 Secondary Efficacy Endpoints

The following secondary efficacy endpoints will be evaluated in the following order using hierarchical fixed sequence testing:

[figure not shown]
1. CFB of Dryness Score (VAS) at Day 15
2. CFB in tCFS (NEI scale) at Day 15
3. CFB of VAS burning/stinging at Day 57
4. CFB in central Corneal Fluorescein Staining (cCFS) (NEI scale) at Day 57

6.4.1.3 Other Pre-specified Efficacy Endpoints

1. CFB of Dryness Score (VAS) at Day 29
2. CFB in tCFS at Day 29
3. CFB in CFS central and inferior sub-regions (NEI scale) to each measured post-baseline visit
4. Proportion of tCFS responders (≥ 3 improvement based on NEI scale) at Day 57
5. Proportion of Dryness Score responders ($\geq 30\%$ improvement from baseline) at Day 57
6. CFB in VAS burning/stinging, sticky feeling foreign body sensation, itching, blurred vision, sensitivity to light, pain, frequency of dryness, and awareness of dry eye symptoms at each measured post-baseline visit
7. CFB in OSDI at each measured post-baseline visit

6.4.2 Safety Variables

1. Ocular and non-ocular AEs
2. logMAR visual acuity
3. Slit-Lamp biomicroscopy observations for lids, cornea, conjunctiva, anterior chamber, iris, and lens
4. Intraocular pressure
5. Dilated fundoscopy

6.5 Statistical Methods

6.5.1 Disposition of Subjects

Tabular summaries will be provided to summarize disposition for the Full Analysis Set (FAS), Per Protocol Set (PPS), and Safety Set (SAF). Reasons for screen failure will be summarized. Subjects included in each of the populations will be summarized overall and by level of stratification factor (clinical site and dryness score) by treatment group and overall. Reasons for exclusion from the analysis populations will be presented by treatment group and overall.

Subject disposition events including randomization, treated, completed study, prematurely discontinued study and/or treatment, and reasons for premature study and/or treatment discontinuation will be summarized by treatment group and overall.

6.5.1.1 Completed Subjects

A completed subject is one who is not a screen failure and has not been discontinued from the trial.

6.5.1.2 Discontinued Subjects

Notification of a subject discontinuation and the reason for study discontinuation will be made to the CRO and/or trial sponsor and will be clearly documented in the eCRF as:

- Adverse event
- Lack of efficacy
- Withdrawal by subject
- Protocol violation

- Lost to follow-up
- Death
- Other

Subjects who discontinue for any reason after randomization will not be replaced.

6.5.2 Protocol Deviations

A deviation from the protocol is an unintended and/or unanticipated departure from the procedures and/or processes approved by the sponsor and the Institutional Review Board (IRB)/Independent Ethics Committee (IEC) and agreed to by the investigator. Deviations will be collected in the CRF. Deviations usually have an impact on individual subjects or a small group of subjects and do not involve inclusion/exclusion or primary endpoint criteria.

Major protocol deviations that could potentially affect the efficacy and result in removal from the PPS will be assessed and identified prior to database lock and unmasking. Major protocol deviations will be summarized by treatment and overall.

6.5.3 Data Sets Analyzed

Inclusion into the Full Analysis Set (FAS) and Safety Set (SAF) will be determined programmatically from the study data collected. Inclusion in the PPS will be determined programmatically from the eCRF data and a blinded Sponsor review.

The statistical analysis of safety data will be performed for the SAF. The analysis of baseline and efficacy data will be performed for the FAS. The primary efficacy analyses will also be performed on the PPS as sensitivity analyses.

A tabulation of the three analysis sets will presented by treatment and overall.

6.5.3.1 Full Analysis Set

The FAS includes all randomized subjects who received at least one dose of investigational product. The primary analysis will be performed on the FAS. Subjects in the FAS will be analyzed as randomized.

6.5.3.2 Per Protocol Set

The PPS includes subjects in the FAS who do not have significant protocol deviations and who complete the study. Protocol deviations will be assessed prior to database lock and unmasking. The PPS will be analyzed using observed data only for efficacy variables. Subjects in the PPS will be analyzed as treated.

6.5.3.2.1 Safety Set

The SAF includes all randomized subjects who have received at least one dose of the investigational product. The SAF will be analyzed for all safety assessments. Subjects in the SAF will be analyzed as treated.

6.5.4 Demographic and Other Baseline Characteristics

Quantitative variables will be summarized using number of subjects (n), mean, median, standard deviation, minimum and maximum. The mean, median, and standard deviation will be presented with one more decimal place than the collected data and the minimum and maximum will be presented with the same decimal places as the collected data. The qualitative variables will be summarized using counts and percentages. All summaries will be presented by treatment group and overall in FAS, PPS, and SAF.

The following demographic and baseline characteristics will be summarized by treatment group and overall:

- Age (years)
- Age category (years) - <18, ≥ 18 to <65, ≥ 65
- Sex
- Race
- Ethnicity
- Iris color
- Eyes qualified for the study – right eye (OD), left eye (OS), both eyes (OU)
- Study Eye – OD, OS

Age will be calculated as (randomization date – date of birth) /365.25.

6.5.4.1 Baseline Ocular Assessments

Baseline ocular assessments will be summarized by treatment and overall for the FAS, PPS, and SAF.

6.5.4.1.1 Dryness Score

Baseline dryness score will be summarized using descriptive statistics by treatment group and overall. Assessment for both eyes is done simultaneously.

6.5.4.1.2 Visual Analog Scale (VAS)

Dry eye symptoms (sticky feeling, burning/stinging, foreign body sensation, itching, blurred vision, sensitivity to light, and pain), awareness of dry eye symptoms and frequency of dryness will be summarized using descriptive statistics by treatment group and overall. Assessment for both eyes is done simultaneously.

6.5.4.1.3 Ocular Surface Disease Index (OSDI)[©]

Baseline OSDI score will be summarized using descriptive statistics by treatment group and overall. Assessment for both eyes is done simultaneously. The OSDI questionnaire consists of 12 questions, with possible answers of 'All of the time', 'Most of the time', 'Half of the time', 'Some of the time' and 'None of the time'. To score the questionnaire, 'All of the time' is given a numerical value of 4, 'Most of the time' a value of 3, 'Half of the time' a value of 2, 'Some of the time' a value of 1, and 'None of the time' a value of 0. The OSDI score is calculated as:

$$\text{OSDI} = \frac{(\text{sum of scores}) \times 25}{(\# \text{ of questions answered})}$$

6.5.4.1.4 Best Corrected Visual Acuity (BCVA)

LogMAR Visual Acuity (VA) will be assessed in the right eye (OD). The procedure will be repeated for the left eye (OS). Subjects should use the most recent correction to attain their best-corrected visual acuity (BCVA). BCVA will be evaluated using the calculated logMAR score. Baseline BCVA of the study eye will be summarized using descriptive statistics by treatment group and overall.

6.5.4.1.5 Slit-Lamp Biomicroscopy

Lids, cornea, conjunctiva, anterior chamber, iris and lens for OD and OS will be examined. Observations will be graded as Normal, Abnormal CS (clinically significant) and Abnormal NCS (not clinically significant). Baseline slit-lamp biomicroscopy results of the study eye will be summarized using descriptive statistics by treatment group and overall.

6.5.4.1.6 Tear Film Break-Up Time (TFBUT)

For each eye, two measurements will be taken and TFBUT will be the average unless the two measurements are >2 seconds apart and are each <10 seconds, in which case, a third measurement would be taken and TFBUT will be the average of the two closest of the three. In all cases, only two values will be entered into the case report form. Baseline TFBUT of the study eye will be summarized using descriptive statistics by treatment group and overall.

6.5.4.1.7 Corneal Fluorescein Staining

Corneal fluorescein staining will be graded with the NEI Grading Scale. A standardized grading system of 0-3 is used for each of the five areas on each cornea. Grade 0 will be specified when no staining is present. The maximum total score for each eye is 15. Baseline corneal fluorescein staining of the study eye will be summarized using descriptive statistics by treatment group and overall.

6.5.4.1.8 Meibomian Gland Assessment (MGD Score)

The secretion of 5 central glands on the lower eyelid will be evaluated for each eye. Each of the 5 glands will be scored from 0-3: 0 = normal, 1 = thick/yellow, whitish, particulate; 2 = paste; 3 = none/occluded. The total score will thus range from 0-15. Baseline MGD score of the study eye will be summarized using descriptive statistics by treatment group and overall.

6.5.4.1.9 Unanesthetized Schirmer's Test I

Schirmer's Tear Test I will be performed ≥ 5 minutes after MGD evaluation. The length of the moistened area of the Schirmer test strip will be recorded (mm) for each eye. Baseline unanesthetized Schirmer's Test I of the study eye will be summarized using descriptive statistics by treatment group and overall.

6.5.4.2 Medical and Surgical History

Medical history, including ocular medical history, will be coded using the Medical Dictionary for Regulatory Activities (MedDRA version 22.1 or higher). Non-ocular medical history will be summarized by system organ class (SOC) and preferred term (PT) by treatment group and overall in the FAS. SOC will be sorted alphabetically. PT will be sorted by descending frequency overall within each SOC. Subjects with a particular medical history event or medical history class will be counted once at the PT level and once at the SOC level. Ocular medical history will be summarized at the subject and eye levels by treatment group and overall in the FAS with separate summaries for the study eye and fellow eye.

Surgical history will not be coded in this trial and thus all data as collected in the CRF will be provided in data listings. Data listings will be provided for medical history as well.

6.5.4.3 Concomitant Medications and Therapies

Concomitant medications will be coded to the Anatomical Therapeutic Chemical (ATC) classification levels 1-4 and preferred terms using the World Health Organization Drug Dictionary (WHODrug B3 Global Sept 2019).

Non-ophthalmic concomitant medications will be summarized by ATC Level 3 (therapeutic subgroup) and preferred term by treatment group and overall in the FAS. ATC Level 3 terms will be sorted alphabetically. Preferred terms will be sorted by descending frequency overall within ATC Level 3 term. Subjects receiving a particular medication or medication of ATC Level 3 will be counted once at the preferred term level and once at ATC Level 3.

Ophthalmic concomitant medications will be summarized at the eye level, separately for study and fellow eyes, and at the subject level by ATC Level 3 and preferred term by treatment group and overall in the FAS.

Concomitant therapies will not be coded in this trial and thus all data as collected in the CRF will be provided in data listings. Data listings will be provided for concomitant medications as well.

6.5.4.3.1 Concomitant Medications

A medication is considered concomitant if the start date is on or after the date of first dose of study drug or if the start date is prior to the first dose of study drug but the end date is after the date of first dose of the study drug. Partial dates will be imputed using the imputation rule specified in section 6.5.8.6.2. If the medication was started prior to first dose of study drug and the stop date is unknown or ongoing, the medication will be considered concomitant. If the start date or stop date is completely missing and it is unclear as to whether the medication is concomitant, the medication will be conservatively assumed as a concomitant medication.

6.5.4.3.2 Concomitant Therapies

A therapy is considered concomitant if the start date is on or after the date of first dose of

study drug or if the start date is prior to the first dose of study drug but the end date is after the date of first dose of the study drug. Partial dates will be imputed using the imputation rule specified in section 6.5.8.6.2. If the therapy was started prior to first dose of study drug and the stop date is unknown or ongoing, the therapy will be considered concomitant. If the start date or stop date is completely and it is unclear as to whether the therapy is concomitant, the therapy will be conservatively assumed as a concomitant therapy.

6.5.5 Measurements of Subject Dosing Compliance

The overall subject dosing compliance will be assessed using the data from the daily dosing diary eCRFs and will be summarized by treatment group in the SAF.

Subject dosing compliance is defined as the proportion of the number of doses administered out of the number of doses that should have been administered per protocol. On the first day of dosing, the expected number of doses will be based on the time of initial dose (24-hour clock) on the 'Dispense Investigational Product' form. If the initial dose in clinic occurs prior to 10:00, then four total doses should be administered that day (morning, lunch time/mid-day, afternoon/early evening, and at bedtime). If the initial dose in clinic occurs between 10:00 and 13:59, then three total doses should be administered that day (lunch time/mid-day, afternoon/early evening, and bedtime). If the initial dose occurs on or after 14:00, then two total doses should be administered that day (afternoon/early evening and bedtime). On the last day of dosing, if the time of last dose (24-hour clock) on the 'Visit Date' form is before 12:00, then only one dose should be administered that day. If the time of last dose (24-hour clock) is on or after 12:00 and before 14:00 then two total doses should be administered that day. If the time of last dose is on or after 14:00 then three total doses should be administered that day. If the last dose is not on the day of the visit, then the time of Dryness Score evaluation will be used to determine the expected number of doses. If the time of Dryness Score is after 12:00 and before 14:00, then only one dose should be administered that day. If the time of Dryness Score is on or after 14:00 and before 16:00, then two total doses should be administered. If the time of Dryness Score is on or after 16:00, then three total doses should be administered. The dosing compliance (%) will be calculated as (total number of doses administered/ total number of doses that should have been administered)*100.

In the event that the dosing diary is not returned, the total number of doses that should have been administered will be adjusted. The days with the dosing diary not returned will be excluded from the denominator. For example, if at Visit 2, 2 days are not returned, exclude those 2 days from the denominator and the number of doses that should have been administered will be adjusted from 56 to 48.

Compliance will be summarized using descriptive statistics in each treatment group and overall in the SAF. Compliance will be presented categorically by treatment group and overall:

- < 50%
- 50-<80%

- 80-<90%
- 90-100%
- >100%-120%
- >120%

6.5.6 Extent of Exposure

Exposure to study drug will be summarized in days. Exposure will be calculated as (last dose date – first dose date + 1). Duration of exposure will be summarized using descriptive statistics in each treatment group and overall in the SAF. Duration of exposure will be presented categorically:

- < 15 days
- 15-<29 days
- 29-<57 days
- ≥ 57 days

Dosing information for each treatment and each subject will be listed. Discontinuation of treatment will be summarized by treatment received. The primary reason for IMP discontinuation will also be summarized by treatment received.

6.5.7 Analysis of Efficacy

6.5.7.1 Descriptive Statistics

Quantitative variables will be summarized using number of subjects (n), mean, median, standard deviation, minimum and maximum. The mean, median, and standard deviation will be presented with one more decimal place than the collected data and the minimum and maximum will be presented with the same decimal places as the collected data. The qualitative variables will be summarized using counts and percentages. Summaries will be presented by treatment group in the FAS and PPS.

All primary and secondary analyses will be two-sided at a significance level of 0.05.

6.5.7.2 Unit of Analysis

For efficacy endpoints, the unit of analysis will be the study eye as defined by the following:

Eyes are eligible for analysis if they meet all of the inclusion criteria. In the case that both eyes are eligible for analysis, the worst eye shall be chosen, and this will be defined as the eye with worse (higher) total corneal staining at Visit 1. If the total corneal staining is the same in both eyes then the right eye will be selected as the study eye.

6.5.7.3 Primary Efficacy Analyses

The primary comparisons in this trial will be between NOV03 versus saline at Day 57 in the FAS with available data per subject using the following estimands

- Endpoint:
 - CFB in tCFS in the study eye at Day 57
 - CFB of Dryness Score (VAS) at Day 57
- Intercurrent event:
 - Discontinuation of study medications is ignored. [treatment policy strategy]
 - Non-optimal compliance is ignored. [treatment policy strategy]
 - Withdrawal due to any reason. Missing data not imputed. [hypothetical strategy if overall study discontinuation rate is <5%]
- Population-level summary:
 - Difference in the mean CFB in tCFS in the study eye at Day 57 between NOV03 and saline
 - Difference in the mean CFB of Dryness Score (VAS) at Day 57 between NOV03 and saline

If the overall study discontinuation rate in the FAS is $\geq 5\%$ then the primary analysis will be based on imputation methodology using the following estimands:

- Endpoint:
 - CFB in tCFS in the study eye at Day 57
 - CFB of Dryness Score (VAS scale) at Day 57
- Intercurrent event:
 - Discontinuation of study medications is ignored. [treatment policy strategy]
 - Non-optimal compliance is ignored. [treatment policy strategy]
 - Withdrawal due to lack of efficacy or adverse events: baseline observation carried forward (BOCF) is used to impute missing data [hypothetical strategy if overall study discontinuation rate $\geq 5\%$]
 - Missing data without withdrawal or withdrawal due to reasons other than lack of efficacy or adverse events: multiple imputations using randomized treatment-based Markov Chain Monte Carlo (MCMC) is used to impute missing data [hypothetical strategy if overall study discontinuation rate $\geq 5\%$]
- Population-level summary:
 - Difference in the mean CFB in tCFS in the study eye at Day 57 between NOV03 and saline
 - Difference in the mean CFB of Dryness Score (VAS scale) at Day 57 between NOV03 and saline

The primary comparison in this trial will be between NOV03 versus saline at Day 57. The primary efficacy endpoints (e.g. CFB in total corneal fluorescein staining [NEI scale] and Dryness Score) will be tested using hierarchical fixed sequence testing and summarized descriptively (n, mean, standard deviation, median, min, and max) and analyzed separately using an ANCOVA model with terms for baseline value, and treatment.

Least squares mean for each treatment group and for the difference between treatment groups will be presented from each model together with two-sided p-values (used for primary inference) and 95% confidence intervals.

Sample SAS ANCOVA code:

```
PROC GLM DATA=INDATA;
  CLASS <TREATMENT>;
  MODEL <ENDPOINT>=<TREATMENT> <BASELINE>;
  LSMEANS <TREATMENT> / CL ALPHA=0.05;
  LSMEANS <TREATMENT> / PDIFF CL ALPHA=0.05;
RUN;
```

Additional robustness analyses will include repeating the primary analysis on the PPS; the FAS imputing missing data using last observation carried forward (LOCF); the FAS imputing missing data using MCMC multiple imputation methodology under different assumptions of missingness (at random and not at random) each using 30 imputed values.

Sample SAS MCMC MI (missing at random):

```
PROC MI DATA=INDATA SEED=97656 OUT=OUTDATA MINIMUM=0 MAXIMUM=3 ROUND=1
NIMPUTE=30;
  MCMC INITIAL=EM;
  BY <TREATMENT>;
  VAR <BASELINE> <PARAMETER>;
RUN;
```

Where <PARAMETER> has 5 levels and refers to the CFS for each region (inferior, superior, central, temporal, and nasal).

Sample SAS MCMC MI (not missing at random):

```
PROC MI DATA=INDATA SEED=36797 OUT=MDATA MINIMUM=0 MAXIMUM=3 ROUND=1
NIMPUTE=30;
```

```
  MCMC IMPUTE=MONOTONE;
  VAR <BASELINE> <PARAMETER>;
RUN;
```

```
PROC MI DATA=MDATA SEED=38549 OUT=OUTDATA2 MINIMUM=. 0 0 MAXIMUM=. 3 3
ROUND=. 1 1;
  CLASS <TREATMENT>;
  MONOTONE REG(<PARAMETER>=<BASELINE> / DETAILS);
  MNAR MODEL(<PARAMETER> / MODELOBs=(<TREATMENT>='Saline'));
  VAR <TREATMENT> <BASELINE> <PARAMETER>;
RUN;
```

Where <PARAMETER> has 5 levels and refers to the CFS for each region (inferior, superior, central, temporal, and nasal).

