10.4.3 Missing Data

The primary analysis will be completed on the FAS with available data per subject, assuming the overall study discontinuation rate is $<5\%$. If the overall study discontinuation rate is $\geq 5\%$ then the primary analysis will be based on the primary imputation methodology as defined [Section 10.4.5](#) and the available data analyses will become robustness analyses.

Additionally, robustness analyses will include repeating the primary analysis on the per protocol set (PPS); the FAS imputing missing data using last observation carried forward (LOCF); the FAS imputing missing data using Markov Chain Monte Carlo (MCMC) multiple imputation methodology under different assumptions of missingness (at random and not at random) each using 30 imputed values.

The imputation model, for each visit, under the assumption of missing **at random** is:

```
PROC MI DATA=INDATA SEED=50048 OUT=OUTDATA1 MINIMUM = 0 MAXIMUM = 3 ROUND  
= 1 NIMPUTE=30;  
  MCMC INITIAL=EM;  
  BY <TREATMENT>;
```

```
VAR <BASELINE> <PARAMETER>;
RUN;
where PARAMETER has 5 levels and refers to the corneal fluorescein staining
score for each region (inferior, superior, central, temporal, and nasal).
The imputation model, for each visit, under the assumption of missing not at
random is:
PROC MI DATA=INDATA SEED=35852 OUT=MDATA MINIMUM = 0 MAXIMUM = 3 ROUND =
1 NIMPUTE=30;
  MCMC IMPUTE=MONOTONE;
  VAR <BASELINE> <PARAMETER>;
RUN;

PROC MI DATA=MDATA SEED=48778 OUT=OUTDATA2 MINIMUM = . 0 0
  MAXIMUM = . 3 3 ROUND = . 1 1;
  CLASS <TREATMENT>;
  MONOTONE REG(<PARAMETER> = <BASELINE> / DETAILS);
  MNAR MODEL(<PARAMETER> / MODELOBS=(<TREATMENT>='Saline'));
  VAR <TREATMENT> <BASELINE> <PARAMETER>;
RUN;
```

where PARAMETER has 5 levels and refers to the corneal fluorescein staining score for each region (inferior, superior, central, temporal, and nasal).

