- **Treatment assignment method** - Subjects who meet all inclusion and exclusion criteria at Visits 0 and 1 will be randomized to a treatment group NOV03 (100% perfluorohexyloctane) or saline (0.6% sodium chloride solution) in a 1:1 ratio stratified by clinical site and dryness score <70 vs ≥ 70 (VAS) at baseline (Visit 1). Subjects who fail to qualify for the trial at screening may be rescreened (see Section 6.2).

An Interactive Response System (IRS) will be used to account for the stratification factors while assigning the drug kit numbers at Visits 1, 2 and 3. Each treatment group of this trial will consist of approximately 280 subjects, such that approximately 250 evaluable subjects per arm complete the trial, for an estimated total of 560 randomized subjects. Specifically, the treatments are defined as follows:

- Treatment 1: NOV03 (100% perfluorohexyloctane), 4 times daily (QID)
- Treatment 2: Saline (0.6% sodium chloride solution), QID
- **Packaging and labeling** - The IMP will be labelled according to the legal requirements and packaged into individual subject kits, each containing 2 bottles of NOV03 or saline solution. In compliance with the Code of Federal Regulations 21 part 312, section 312.6, the labels for the IMP shall be comprised of:
 - Protocol number
 - Kit number
 - Investigational new drug statement
 - Storage conditions
 - Name and address of the sponsor
- **Trial configuration** - This is a parallel trial design (NCI Preferred Term ‘Parallel Study’). Subjects will be randomized to either NOV03 QID or saline QID in a 1:1 ratio. Subjects will self-administer one drop of masked investigation product in the lower cul-de-sac of each eye QID at approximately the same time e.g., morning, lunch time/midday, afternoon/early evening, and at bedtime. *Note:* if a dose is missed, the next dose should be administered on time.
- **Type of control used** - This is a saline-controlled (NCI Preferred Term ‘Placebo Control’), superiority trial.
- **Duration of the trial** - The estimated trial duration is approximately 8 months, from first subject first visit to last subject last visit. An individual subject’s participation will involve 5 visits over approximately a 10-week period, including screening. After the trial, subjects will be treated according to standard of care, at the discretion of the treating physician.

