6.5.10 Determination of Sample Size

The statistical hypotheses for the primary endpoint of CFB corneal fluorescein staining (NEI scale) total score at Day 57 are as follows:

H_{01} : The difference, between study eyes treated with NOV03 and study eyes treated with saline, in the mean CFB corneal fluorescein staining (NEI scale) total score at Day 57 = 0.

H_{A1} : The difference, between study eyes treated with NOV03 and study eyes treated with saline, in the mean CFB corneal fluorescein staining (NEI scale) total score at Day 57 \neq 0, with superiority claimed if the difference is less than 0 (NOV03 minus saline).

The statistical hypotheses for the hierarchical primary endpoint of the CFB Dryness Score at Day 57 are as follows:

H_{02} : The difference, between subjects treated with NOV03 and subjects treated with saline, in the mean CFB Dryness Score at Day 57 = 0.

H_{A2} : The difference, between subjects treated with NOV03 and subjects treated with saline, in the mean CFB Dryness Score at Day 57 $\neq 0$, with superiority claimed if the difference is less than 0 (NOV03 minus saline).

Two hundred fifty (250) subjects (study eyes) per treatment group yields 97.9% power to reject H_{01} in favor of H_{A1} and conclude superiority of NOV03 over saline in the mean CFB tCFS score at Day 57 assuming a true difference (NOV03 minus saline) of -1.0, a common standard deviation of 2.8, and a two-sided alpha = 0.05. Two hundred fifty (250) subjects per treatment group yields 97.9% power to reject H_{02} in favor of H_{A2} and conclude superiority of NOV03 over saline in the mean CFB Dryness Score (VAS) at Day 57 assuming a true difference (NOV03 minus saline) of -10, a common standard deviation of 28, and a two-sided alpha = 0.05. Accounting for an assumed 10% subject discontinuation rate, approximately 560 subjects (280 subject each arm) will be randomly assigned to trial treatment such that approximately 250 evaluable participants per arm complete the trial.

Therefore, assuming independence between tCFS score and Dryness Score (VAS), 250 FAS subjects per treatment group at Day 57 yields $97.9\% * 97.9\% = 95.8\%$ power to reject both H_{01} and H_{02} . A positive correlation between these two endpoints would increase the overall power.

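### As printed, the tCFS multiple-imputation code treats the five corneal regions separately; if regional scores are positively correlated, MI standard errors for the summed total are modestly too small

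*SAP*

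**What the plan says.** SAP 6.5.7.3 prints two blocks of sample code for multiple imputation (MI). The at-random block runs by treatment, lists one baseline and one parameter as variables, limits values to 0-3 and rounds to whole grades. The parameter "has 5 levels and refers to the CFS for each region (inferior, superior, central, temporal, and nasal". The not-at-random block ends with a step on treatment, one baseline and one parameter, with matching limits: "OUT=OUTDATA2 MINIMUM=. 0 0 MAXIMUM=. 3 3". Its regression statement predicts the parameter from baseline alone. Protocol 10.4.3 prints the same structure and says "where PARAMETER has 5 levels and refers to the corneal fluorescein staining score for each region (inferior, superior, central, temporal, and nasal".

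Both documents define total staining as the sum of the five regional grades (inclusion criterion 8; SAP 6.5.4.1.7), but neither writes out the step that sums imputed regions.

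The code stands among the robustness analyses. If discontinuation in the FAS is 5% or more, MI also enters the primary analysis: withdrawals for lack of efficacy or adverse events take their baseline value (BOCF), and for the remaining missing data "multiple imputations using randomized treatment-based Markov Chain Monte Carlo (MCMC) is used to impute missing data". SAP 6.5.7.4.1 carries the same rule to the secondary endpoints, which include tCFS at Day 15.

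**The concern.** A subject who misses the Day 57 examination has no grade in any region. If each region is drawn in its own run, given only its own baseline, the five draws are independent of one another. Real regional grades in one eye would be expected to rise and fall together. A total built from independent draws therefore spreads less than a real total, both within each completed data set and between imputations. Rubin's rules combine both components, so the standard error comes out too small.

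This is the only MI model printed, and its 0-3 limits fit regional staining grades only. tCFS at Day 57 is tested first and gates the Dryness Score and every secondary endpoint, so an understated standard error there could pass a borderline result down the whole sequence.

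**Working it through.** **The plan's own figure.** SAP 6.5.10 states "Two hundred fifty (250) subjects (study eyes) per treatment group yields 97.9% power", "assuming a true difference (NOV03 minus saline) of -1.0, a common standard deviation of 2.8, and a two-sided alpha = 0.05". The standard error is 2.8 × √(2/250) = 0.2504, so 1.0/0.2504 = 3.993 and power is Φ(3.993 − 1.960) = 97.9%. For both endpoints, 0.979² = 95.8%. "Accounting for an assumed 10% subject discontinuation rate", 250/0.9 = 278, and 280 × 0.9 = 252. The sample size reproduces and is not in question.

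**What each run handles.** The not-at-random step gives three limits for three variables, so it holds one region. The baseline limit of 3 shows that the baseline is regional too, because entry requires a total of 4 to 11. The at-random block uses the same placeholders and definition, but its single limits would also be valid for a list of all regions.

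**Variance lost.** Let each regional change have SD s, with common between-region correlation ρ, and let the total change have SD S.

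- Correct variance: S² = 5s²(1 + 4ρ), so ρ = (S²/(5s²) − 1)/4.
- Variance from independent draws: 5s².
- Ratio: r = 5s²/S² = 1/(1 + 4ρ).

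S = 2.8 is the planning value. S = 2.5 is the NVU-002 estimate in the Protocol synopsis. Neither s nor ρ is documented; s = 0.8 to 1.0 is an assumption. The change-score correlation stands in for the correlation given baseline.

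**Effect on the standard error.** With share m imputed at random and 30 imputations, the Rubin variance relative to complete data is T = (1 − m) + m·r + r·[m/(1 − m)]·(1 + 1/30). The correct value sets r = 1. The true sampling variance is 1/(1 − m), so type I error is 2Φ(−1.96·√[T(1 − m)]).

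Example with S = 2.8, s = 0.8, m = 0.10: r = 3.2/7.84 = 0.408; T = 0.900 + 0.041 + 0.047 = 0.988, against 1.115 when r = 1. The SE ratio is √(0.988/1.115) = 0.941 and type I error is 6.5%. T is below 1, so losing 10% of the data appears to add precision.

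| S | s | ρ | r | SE ratio, 10% imputed | Type I, 10% | SE ratio, 5% imputed | Type I, 5% |
|---|---|---|---|---|---|---|---|
| 2.8 | 0.8 | 0.36 | 0.41 | 0.941 | 6.5% | 0.970 | 5.7% |
| 2.8 | 1.0 | 0.14 | 0.64 | 0.964 | 5.8% | 0.982 | 5.4% |
| 2.5 | 0.8 | 0.24 | 0.51 | 0.952 | 6.2% | 0.976 | 5.6% |
| 2.5 | 1.0 | 0.06 | 0.80 | 0.981 | 5.4% | 0.990 | 5.2% |

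The effect vanishes at ρ = 0, which needs s = S/√5: 1.25 for S = 2.8, 1.12 for S = 2.5.

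**Simulation.** 280 per arm, five 0-3 grades, baseline total 4 to 11, change SD 2.7 to 2.8, missing completely at random, 30 imputations by arm, ANCOVA, Rubin's rules, 1,000 trials per setting. Separate imputation (with limits and rounding) was compared with joint imputation (without them).

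| Setting | Mean SE, separate / joint | Rejection under the null, separate / joint |
|---|---|---|
| ρ = 0.32, 10% imputed | 0.221 / 0.236 | 6.6% / 5.4% |
| ρ = 0.15, 10% imputed | 0.209 / 0.221 | 5.1% / 3.9% |
| ρ = 0.32, 5% imputed | 0.222 / 0.229 | 5.0% / 3.8% |

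Rejection rates carry Monte Carlo error of about 0.7 points, so their absolute levels are imprecise; the SE comparison is the firmer evidence. In the top row, the SE with no data missing was 0.223, above the 0.221 from separate imputation. The variance of change in imputed subjects was 0.54 of that in observed subjects, against 1.06 with joint imputation.

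**Role of limits and rounding.** In the top-row setting, separate imputation without limits or rounding also gave a mean SE of 0.221. With a true effect near −1.06, adding them moved the estimate from −1.064 to −1.054.

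**The case against.** The strongest reply is that the code is labelled a sample, uses placeholders, and leaves out the summing step. The three-limit list that settles the reading belongs to the not-at-random step. The block that matches the by-treatment imputation of the primary branch is the at-random one, and a programmer could list all regions there. This stands in part: for that block the point is the natural reading, not a proven error. But the shared definition of the parameter points to one region per run, and nothing in either document asks for joint imputation.

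Three further points stand:

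- The correlation is not reported. The planning SD of 2.8 is deliberately conservative, and the NVU-002 value of 2.5 gives a smaller effect.
- A reader might apply the whole assumed 10% discontinuation to MI in the primary analysis. The documents do not support that, because withdrawals for lack of efficacy or adverse events go to BOCF. If half went there (an assumption), about 5% would be imputed.
- The available-data ANCOVA, LOCF, per-protocol, t-test, Wilcoxon and repeated-measures analyses are all planned and do not use this code. An over-narrow MI interval would appear beside them.

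A reader might also blame the 0-3 limits and rounding for the small standard errors. The simulation does not support this: the loss is the same without them, and their own effect is a slight shift toward zero.

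**Conclusion.** The point holds in direction and is modest in size. Followed as printed and summed, the code drops between-region covariance and understates the MI standard error for tCFS whenever regional scores are positively correlated. Under the assumed ranges, the at-random SE is about 2 to 6% too small and type I error about 5.4 to 6.5% with 10% imputed; with 5% imputed, about 1 to 3% and 5.2 to 5.7%. The size under the not-at-random model was not calculated.

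It would be wrong to infer that the primary test as planned exceeds 5% type I error. That requires discontinuation of 5% or more, separate coding, positive correlation, and a material share of missing data outside BOCF. Below 5% discontinuation, only the robustness analyses are touched. Central staining alone is not a sum and does not have this problem.

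At roughly the planned effect nothing changes: simulated power was 99.8% with separate and 99.7% with joint imputation. A borderline result could change. With 10% imputed, a correct p of 0.05 would be reported as about 0.037 (1.96/0.941 = 2.08) to 0.046 (1.96/0.981 = 2.00). On the endpoint that gates all the others, that merits correction before unmasking.

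**What to change.** State in SAP 6.5.7.3 and Protocol 10.4.3 that missing tCFS is imputed in one of two ways, and apply the choice to the at-random, not-at-random and primary (5% or more) analyses:

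- impute the total directly by arm, with cCFS in its own model; or
- put all five regional baselines and scores in one VAR list, sum the completed regions, and combine by Rubin's rules.

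With the first option the 0-3 limits must be removed, since they do not fit a 0-15 total. With the second, dropping limits and rounding is optional. In the not-at-random step the regression statement must also carry the other regions, because as printed it conditions on baseline alone and a longer VAR list would not restore the covariance.

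The cost is a few lines of code and text, and an MI confidence interval for tCFS about 2 to 6% wider with 10% imputed (1/0.981 to 1/0.941).
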